4. SELECTION OF STUDY POPULATION

4.1. Inclusion Criteria for Parts A: Healthy Subjects

Subjects for Part A must satisfy all of the following criteria at the Screening visit unless otherwise stated:

1. Males or females, of any race, between 18 and 55 years of age, inclusive.
2. Body mass index (BMI) of 18.0 to 32.0 kg/m² (inclusive) with a minimum body weight of 50 kg.
3. In good health, determined by no clinically significant findings from medical history, physical examination, 12-lead ECG, vital signs measurements, and clinical laboratory evaluations (congenital nonhaemolytic hyperbilirubinemia [eg, suspicion of Gilbert's syndrome based on total and direct bilirubin] is not acceptable) at Screening and Check-in as assessed by the Investigator (or designee), as applicable.
4. Resting heart rate \geq 45 bpm and \leq 90 bpm with a single 12-lead ECG at Screening.
5. Females will not be pregnant or lactating, and females of childbearing potential and males will agree to use contraception as detailed in [Appendix 4](#).

6. Male subjects must agree to refrain from sperm donation and females should refrain from ova donation from the date of Check-in (Day -1) until 90 days after the Follow-up visit.
7. Able to comprehend and willing to sign an ICF and to abide by the study restrictions.

4.2. Inclusion Criteria for Part B: Healthy Subjects

Subjects for Part B must satisfy all of the following criteria at the Screening visit unless otherwise stated:

1. Males or females, of any race, between 18 and 60 years of age, inclusive.
2. Body mass index (BMI) of 18.0 to 32.0 kg/m² (inclusive) with a minimum body weight of 50 kg.
3. In good health, determined by no clinically significant findings from medical history, physical examination, 12-lead ECG, vital signs measurements, and clinical laboratory evaluations (congenital nonhaemolytic hyperbilirubinemia [eg, suspicion of Gilbert's syndrome based on total and direct bilirubin] is not acceptable) at Screening and Check-in as assessed by the Investigator (or designee), as applicable.
4. Females will not be pregnant or lactating, and females of childbearing potential and males will agree to use contraception as detailed in [Appendix 4](#).
5. Male subjects must agree to refrain from sperm donation and females should refrain from ova donation from the date of Check-in (Day -1) until 90 days after the Follow-up visit.
6. Able to comprehend and willing to sign an ICF and to abide by the study restrictions.

4.3. Inclusion Criteria for Part C: Subjects with Suspected NASH and Liver Fibrosis

Subjects for Parts C must satisfy all of the following criteria at the Screening visit unless otherwise stated:

1. Males or females, of any race, between 18 and 60 years of age, inclusive.
2. Body mass index (BMI) of ≥ 25.0 and ≤ 38.0 kg/m².
3. Documented history of fatty liver within the last 24 weeks by one of the following: magnetic resonance imaging (MRI) suggesting liver fat $\geq 8\%$, ultrasound (US) indicating fatty liver, or Fibroscan Controlled Attenuation Parameter (CAP) > 270 dB/m. In subjects without a documented history of fatty liver, a Fibroscan CAP or US can be performed at Screening. Subjects with Fibroscan CAP > 270 dB/m or US indicating fatty liver are eligible.
4. Metabolic syndrome (Adult Treatment Panel III definition) or T2DM (defined as stable diabetes with glycosylated haemoglobin [HbA1c] $\leq 9.5\%$).
5. Alanine aminotransferase (ALT) ≥ 20 U/L for females and ≥ 30 U/L for males at Screening.
6. Fibroscan ≥ 7 KPa and < 13 KPa, or Fibrosis-4 (FIB-4) index ≥ 1.1 and < 3.25 .

7. Females of nonchildbearing potential defined as permanently sterile (ie, due to hysterectomy, bilateral salpingectomy, and/or bilateral oophorectomy) or postmenopausal (defined as at least 12 months postcessation of menses without an alternative medical cause and follicle-stimulating hormone [FSH] level ≥ 40 mIU/mL). Males will agree to use contraception as detailed in [Appendix 4](#).
8. Male subjects must agree to refrain from sperm donation and females should refrain from ova donation from the date of Check-in (Day -1) until 90 days after the Follow-up visit.
9. Able to comprehend and willing to sign an ICF and to abide by the study restrictions.

4.4. Exclusion Criteria for Part A: Healthy Subjects

Subjects from Part A will be excluded from the study if they satisfy any of the following criteria at the Screening visit unless otherwise stated:

1. Significant history or clinical manifestation of any metabolic, allergic, dermatological, hepatic, renal, haematological, pulmonary, cardiovascular, gastrointestinal, neurological, respiratory, endocrine, or psychiatric disorder, as determined by the Investigator (or designee).
2. History of febrile illness within 7 days prior to the first dose of study drug or subjects with evidence of active infection.
3. History of significant hypersensitivity, intolerance, or allergy to any drug compound, food, or other substance, unless approved by the Investigator (or designee).
4. History of stomach or intestinal surgery or resection that would potentially alter absorption and/or excretion of orally administered drugs (uncomplicated appendectomy and hernia repair will be allowed, but not cholecystectomy).
5. Any of the following:
 - a. QTcF > 450 msec confirmed by repeat measurement.
 - b. QRS duration > 110 msec confirmed by repeat measurement.
 - c. PR interval > 220 msec confirmed by repeat measurement.
 - d. findings which would make QTc measurements difficult or QTc data uninterpretable.
 - e. history of additional risk factors for torsades de pointes (eg, heart failure, hypokalaemia, family history of long QT syndrome).
6. History of alcoholism or drug/chemical abuse within 1 year prior to Check-in.
7. Alcohol consumption of > 21 units per week for males and > 14 units per week for females. One unit of alcohol equals $\frac{1}{2}$ pint (285 mL) of beer or lager, 1 glass (125 mL) of wine, or $\frac{1}{6}$ gill (25 mL) of spirits.
8. Positive alcohol breath test result or positive urine drug screen (confirmed by repeat) at Screening or Check-in.

9. Positive hepatitis panel and/or positive human immunodeficiency virus (HIV) test ([Appendix 2](#)).
10. Participation in a clinical study involving administration of an investigational agent or vaccine (new chemical entity) or having received a biological product in the past 90 days prior to dosing.
11. Use or intend to use any medications/products known to alter drug absorption, metabolism, or elimination processes, including St. John's wort, within 30 days prior to dosing, unless deemed acceptable by the Investigator (or designee).
12. Use or intend to use any prescription medications/products other than hormone replacement therapy, oral, implantable, transdermal, injectable, or intrauterine contraceptives within 14 days prior to dosing, unless deemed acceptable by the Investigator (or designee).
13. Use or intend to use slow-release medications/products considered to still be active within 14 days prior to Check-in, unless deemed acceptable by the Investigator (or designee).
14. Use or intend to use any nonprescription medications/products including vitamins, minerals, and phytotherapeutic/herbal/plant-derived preparations within 7 days prior to Check-in, unless deemed acceptable by the Investigator (or designee).
15. Use of tobacco- or nicotine-containing products within 3 months prior to Check-in, or positive cotinine at Screening or Check-in.
16. Receipt of blood products within 2 months prior to Check-in and donation of blood from 3 months prior to Screening, plasma from 2 weeks prior to Screening, or platelets from 6 weeks prior to Screening.
17. Poor peripheral venous access.
18. Have previously completed or withdrawn from this study investigating GB1211, and have previously received the investigational product.
19. Subject who, in the opinion of the Investigator (or designee), should not participate in this study.
20. Subject is not willing to minimise or avoid exposure to natural or artificial sunlight (tanning beds or UVA/B treatment) following administration of study drug until 24 hours after the last dose.

4.5. Exclusion Criteria for Part B: Healthy Subjects

Subjects from Part B will be excluded from the study if they satisfy any of the following criteria at the Screening visit unless otherwise stated:

1. Significant history or clinical manifestation of any metabolic, allergic, dermatological, hepatic, renal, haematological, pulmonary, cardiovascular, gastrointestinal, neurological, respiratory, endocrine, or psychiatric disorder, as determined by the Investigator (or designee).

2. History of febrile illness within 7 days prior to the first dose of study drug or subjects with evidence of active infection.
3. History of significant hypersensitivity, intolerance, or allergy to any drug compound, food, or other substance, unless approved by the Investigator (or designee).
4. History of stomach or intestinal surgery or resection that would potentially alter absorption and/or excretion of orally administered drugs (uncomplicated appendectomy and hernia repair will be allowed, but not cholecystectomy).
5. Clinically significant ECG abnormalities or QTcF greater than 450 msec for males and 470 msec for females at either Screening or Day 1 predose, or any prior history of QT abnormality.
6. History of alcoholism or drug/chemical abuse within 1 year prior to Check-in.
7. Alcohol consumption of > 21 units per week for males and > 14 units per week for females. One unit of alcohol equals ½ pint (285 mL) of beer or lager, 1 glass (125 mL) of wine, or 1/6 gill (25 mL) of spirits.
8. Positive alcohol breath test result or positive urine drug screen (confirmed by repeat) at Screening or Check-in.
9. Positive hepatitis panel and/or positive HIV test ([Appendix 2](#)).
10. Participation in a clinical study involving administration of an investigational agent or vaccine (new chemical entity) or having received a biological product in the past 90 days prior to dosing.
11. Use or intend to use any medications/products known to alter drug absorption, metabolism, or elimination processes, including St. John's wort, within 30 days prior to dosing, unless deemed acceptable by the Investigator (or designee).
12. Use or intend to use any prescription medications/products other than hormone replacement therapy, oral, implantable, transdermal, injectable, or intrauterine contraceptives within 14 days prior to dosing, unless deemed acceptable by the Investigator (or designee).
13. Use or intend to use slow-release medications/products considered to still be active within 14 days prior to Check-in, unless deemed acceptable by the Investigator (or designee).
14. Use or intend to use any nonprescription medications/products including vitamins, minerals, and phytotherapeutic/herbal/plant-derived preparations within 7 days prior to Check-in, unless deemed acceptable by the Investigator (or designee).
15. Use of tobacco- or nicotine-containing products within 3 months prior to Check-in, or positive cotinine at Screening or Check-in.
16. Receipt of blood products within 2 months prior to Check-in and donation of blood from 3 months prior to Screening, plasma from 2 weeks prior to Screening, or platelets from 6 weeks prior to Screening.
17. Poor peripheral venous access.

18. Have previously completed or withdrawn from this study investigating GB1211 and have previously received the investigational product
19. Subject who, in the opinion of the Investigator (or designee), should not participate in this study.
20. Subject is not willing to minimise or avoid exposure to natural or artificial sunlight (tanning beds or UVA/B treatment) following administration of study drug until 24 hours after the last dose.

4.6. Exclusion Criteria for Part C: Subjects with Suspected NASH and Liver Fibrosis

Subjects from Part C will be excluded from the study if they satisfy any of the following criteria at the Screening visit unless otherwise stated:

1. If diabetic and diabetes is other than T2DM.
2. Subjects, who have had bariatric surgery of any kind or, in the opinion of the Investigator, have experienced a clinically significant change in body weight within the 3 months prior to Screening.
3. History of any known serious disease (such as cancer, except skin basocellular carcinomas, major infection, clinically significant gastrointestinal disorder, major autoimmune disease) or other disease which in the Investigator's opinion would exclude the patient from the study.
4. The following clinical laboratory results at Screening:
 - Total Bilirubin $> 2 \times$ ULN
 - ALT > 155 U/L for females and > 185 U/L for males
 - AST > 155 U/L for females and > 200 U/L for males
5. Other abnormal clinical laboratory values that are considered clinically significant for this population.
6. History of febrile illness within 7 days prior to the first dose of study drug or subjects with evidence of active infection.
7. History of significant hypersensitivity, intolerance, or allergy to any drug compound, food, or other substance, unless approved by the Investigator (or designee).
8. History of stomach or intestinal surgery or resection that would potentially alter absorption and/or excretion of orally administered drugs (uncomplicated appendectomy, cholecystectomy, and hernia repair will be allowed).
9. Clinically significant ECG abnormalities or QTcF greater than 450 msec for males and 470 msec for females at either Screening or Day 1 predose, or any prior history of QT abnormality.
10. History of alcoholism or drug/chemical abuse within 1 year prior to Check-in.
11. Alcohol consumption of > 14 units per week for males and for females. One unit of alcohol equals $\frac{1}{2}$ pint (285 mL) of beer or lager, 1 glass (125 mL) of wine, or $\frac{1}{6}$ gill (25 mL) of spirits.

12. Positive alcohol breath test result or positive urine drug screen (confirmed by repeat) at Screening or Check-in.
13. Positive hepatitis panel and/or positive HIV test ([Appendix 2](#)).
14. Clinically significant laboratory abnormalities, as determined by the Investigator.
15. A creatinine clearance of less than 50 mL/min (as calculated by Cockcroft-Gault equation) or estimated glomerular filtration rate (eGFR) < 60 mL/[min*1.73 m²] at Screening.
16. Participation in a clinical study involving administration of an investigational agent or vaccine (new chemical entity) or having received a biological product in the past 90 days prior to dosing.
17. Use or intend to use any medications/products known to alter drug absorption, metabolism, or elimination processes, including St. John's wort, within 30 days prior to dosing, unless deemed acceptable by the Investigator (or designee).
18. Use or intend to use slow-release medications/products considered to still be active within 14 days prior to Check-in, unless deemed acceptable by the Investigator (or designee).
19. Subject taking any antidiabetic medications, with the exception of metformin, sulfonylureas, gliptins, and sodium/glucose co-transporter 2 inhibitors, within 3 months prior to Screening.
20. Use of any of the following non-permitted medication within 6 months prior to Screening: amiodarone, bile salt chelators, methotrexate, pharmacological doses of systemic corticosteroids for at least 2 consecutive weeks, or any other medications known to affect liver function.
21. Use or intend to use any nonprescription medications/products including vitamins (Vitamin E at dose <400 U is permitted, Vitamin E at dose 400 U is allowed if on a stable dose for 2 months prior), minerals, and phytotherapeutic/herbal/plant-derived preparations within 7 days prior to Check-in, unless deemed acceptable by the Investigator (or designee).
22. Receipt of blood products within 2 months prior to Check-in and donation of blood from 3 months prior to Screening, plasma from 2 weeks prior to Screening, or platelets from 6 weeks prior to Screening.
23. Poor peripheral venous access.
24. Have previously completed or withdrawn from this study investigating GB1211, and have previously received the investigational product.
25. Subject who, in the opinion of the Investigator (or designee), should not participate in this study.
26. Subject is not willing to minimise or avoid exposure to natural or artificial sunlight (tanning beds or UVA/B treatment) following administration of study drug until 24 hours after the last dose.

For Parts A and B, subjects may previously have been screened on a generic basis to determine their eligibility for inclusion in Phase I clinical studies conducted at the CRU. If generic screening was performed within the specified study screening window, selected study-specific procedures will be repeated either at an additional Screening visit or on admission to the CRU on Day -1.

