4.5	Addition of exclusion criterion 20: Subject is not willing to minimise or avoid exposure to natural or artificial sunlight (tanning beds or UVA/B treatment) following administration of study drug until 24 hours after the last dose.
4.6	Addition of exclusion criterion 26: Subject is not willing to minimise or avoid exposure to natural or artificial sunlight (tanning beds or UVA/B treatment) following administration of study drug until 24 hours after the last dose.
6.6	An additional section was added to Section 6:

	
6.6. Exposure to Ultraviolet Light
 
Subjects should minimise or avoid exposure to natural or artificial sunlight (tanning beds or UVA/B treatment) following administration of study drug until 24 hours after the last dose. If subjects need to be outdoors during this period, they should wear loose fitting clothes that protect skin from sun exposure and discuss other sun protection measures with the Investigator.

--	--

STUDY IDENTIFICATION

Sponsor	Galecto Biotech [name] [name] [name] Denmark
Sponsor's Study Contact	 Chief Medical Officer Galecto Biotech [name] [name] [name] Denmark
Medical Monitor	 Covance [name] [name] [name] [name] UK 
Study Site (Parts A and B)	Covance Clinical Research Unit Ltd. [name] [name] [name] UK
Part C Study Site(s) and Investigator(s)	Study site(s) and Investigator(s) in the EU
Principal Investigator (Parts A and B)	 Covance Clinical Research Unit Ltd. [name] [name] [name] UK 
Clinical Laboratory (Parts A and B)	Covance Clinical Pathology Services [name] [name] UK
Bioanalytical Laboratory	Covance Laboratories Ltd

[name]
[name]
UK

Statistician

Covance Biometrics

SYNOPSIS

Title of study: GB1211 – A Randomised, Double-Blind, Placebo-Controlled, First-In-Human, Study of Orally Administered GB1211 to Evaluate the Safety, Tolerability, and Pharmacokinetics of Single Ascending Doses (SAD) and Multiple Ascending Doses (MAD) in Healthy Subjects and in Subjects with Suspected Nonalcoholic Steatohepatitis (NASH) and Liver Fibrosis

Objectives:

The primary objectives of the study are:

- to evaluate the safety and tolerability of single and multiple doses of GB1211 administered to healthy subjects.

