3. INVESTIGATIONAL PLAN

This is a Phase 1, randomised, double-blind, placebo-controlled, first-in-human study in which the safety, tolerability, and PK of orally administered GB1211 will be assessed in healthy adult subjects and adult subjects with suspected NASH and liver fibrosis.

Suspected NASH is defined as the presence or history of fatty liver, together with elevated alanine aminotransferase (ALT; defined as ALT values ≥ 30 U/L in males or ≥ 20 U/L in females), plus either confirmed type 2 diabetes mellitus (T2DM) or metabolic syndrome (Adult Treatment Panel III definition), in the absence of any other liver disease. Additional criteria aim to enrich for individuals with liver fibrosis (as per inclusion criteria; [Section 4.3](#)).

The study will consist of 3 parts: a SAD phase (Part A) enrolling a total of 5 cohorts of healthy subjects; a MAD phase (Part B) enrolling 2 cohorts of healthy subjects; and an optional Part C MAD phase, enrolling 1 cohort of subjects with suspected NASH and liver fibrosis. One cohort of Part A will receive GB1211 under both fasted and fed conditions to investigate the effect of food.

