4.8. Subject Withdrawal and Replacement

A subject is free to withdraw from the study at any time. In addition, a subject will be withdrawn if any of the following criteria are met:

- change in compliance with any inclusion/exclusion criterion that is clinically relevant and affects subject safety as determined by the Investigator (or designee).
- noncompliance with the study restrictions that might affect subject safety or study assessments/objectives, as considered applicable by the Investigator (or designee).
- any clinically relevant sign or symptom that, in the opinion of the Investigator (or designee), warrants subject withdrawal.

In the event of confirmed results for any of the following criteria, dosing of a subject with the IMP will be stopped permanently:

- QTcF increases > 60 msec compared to baseline (predose) and/or absolute QTcF values > 500 msec (confirmed by repeat measurement).
- Systemic exposure for any individual subject is predicted to exceed a C_{max} of 19755 ng/mL and/or an AUC_{0-24} of 52486 ng.h/mL; ie, systemic exposure will be no greater than the lowest exposure at the NOAEL.
- Liver chemistry results:
 1. ALT or AST > 5 x ULN, which is confirmed by repeat
 2. ALT or AST > 3 x ULN, which is confirmed and total bilirubin > 2 x ULN or international normalised ratio >1.5
 3. ALT or AST > 3 x ULN, which is confirmed and the new appearance (ie, onset coincides with the changes in hepatic enzymes) of fatigue, nausea, vomiting, right upper quadrant pain or tenderness, fever, rash,

or eosinophilia (> ULN) felt by the Investigator to be potentially related to hepatic inflammation/injury.

If a subject is withdrawn, the Sponsor will be notified and the date and reason(s) for the withdrawal will be documented in the subject's electronic Case Report Form (eCRF). If a subject is withdrawn, efforts will be made to perform all follow-up assessments, if possible ([Appendix 6](#)). Other procedures may be performed at the Investigator's (or designee's) and/or Sponsor's discretion. If the subject is in-house, these procedures should be performed before the subject is discharged from the clinic. The Investigator (or designee) may also request that the subject return for an additional Follow-up visit. All withdrawn subjects will be followed until resolution of all their AEs or until the unresolved AEs are judged by the Investigator (or designee) to have stabilised.

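### Part C caps ALT and AST at entry in fixed U/L but stops dosing at 5 x ULN, so a laboratory with a low ULN can admit a subject already above the stop level

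*Protocol*

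**What the plan says.** **Entry (Protocol 4.6, criterion 4).** Under "The following clinical laboratory results at Screening", Part C excludes total bilirubin above 2 x ULN, "ALT > 155 U/L for females and > 185 U/L for males" and "AST > 155 U/L for females and > 200 U/L for males". Bilirubin is expressed as a multiple of the ULN; the two transaminases are not.

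**Stopping (Protocol 4.8).** "In the event of confirmed results for any of the following criteria, dosing of a subject with the IMP will be stopped permanently". The first liver criterion is "ALT or AST > 5 x ULN, which is confirmed by repeat". The second requires ALT or AST above 3 x ULN, "which is confirmed and total bilirubin > 2 x ULN or international normalised ratio >1.5". The third requires ALT or AST above 3 x ULN with new hepatic symptoms or eosinophilia. There is no exception for Part C and no rule relative to the subject's own baseline.

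**Laboratory.** The Study Identification table names a clinical laboratory for Parts A and B only and gives Part C as "Study site(s) and Investigator(s) in the EU". Appendix 2 lists the analytes without reference ranges. No ALT or AST ULN appears in either document.

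**Other safeguards.** Criteria 14 and 25 of section 4.6 allow exclusion on the Investigator's judgement. Appendix 6, Table 3 repeats the eligibility check and the laboratory panel on Day -1. Section 7.3.2 requires clinical assessment of all laboratory data and permits extra tests.

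**The concern.** The entry and stopping limits are on different scales and can be compared only once a laboratory's ULN is known. Where that ULN is low, the numeric entry criteria and the stopping rule disagree about the same subject: one lets the subject in at an enzyme level at which the other ends dosing for good. The protocol does not say which governs before the first dose.

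Two things are at stake. The first is safety in the first patient cohort: a subject could start dosing at a level the protocol itself treats as a reason to stop. The second is interpretation: a stop triggered by a high baseline would meet the same rule as a drug effect, in a cohort with only 15 subjects on GB1211 and 10 on placebo.

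**Working it through.** **1. Break-even ULN.** Exclusion is by strict inequality, so the highest admissible value is the ceiling itself. It exceeds the stop only if ceiling > 5 x ULN, that is, if ULN < ceiling / 5.

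- Female ALT and AST: 155 / 5 = 31 U/L
- Male ALT: 185 / 5 = 37 U/L
- Male AST: 200 / 5 = 40 U/L

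**2. Admissible values above the stop.** Band width = max(0, ceiling - 5 x ULN). The ULN is an assumption, varied here because the documents give none.

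| Assumed ULN (U/L) | 5 x ULN | Female ALT, AST | Male ALT | Male AST |
|---|---|---|---|---|
| 30 | 150 | 5 (150-155) | 35 (150-185) | 50 (150-200) |
| 35 | 175 | 0 | 10 (175-185) | 25 (175-200) |
| 37 | 185 | 0 | 0 | 15 (185-200) |
| 40 or more | 200 or more | 0 | 0 | 0 |

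**3. Exposure before the first scheduled on-treatment test.** Planned dosing is twice daily from Day 1 (section 3.1.3). The first scheduled on-treatment panel is on Day 14, before the morning dose (Appendix 6, Table 3). Days 1 to 13 give 13 x 2 = 26 planned doses.

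**4. Expected number.** All distributional inputs are assumptions: log-normal ALT with median 40, 60 or 80 U/L, between-subject CV 50% or 80%, and within-subject CV 10%, 20% or 30%, making 18 settings of 600,000 simulated subjects each. A subject is admitted if Screening ALT lies between the section 4.3 floor (30 male, 20 female) and the ceiling (185 male, 155 female). The quantity of interest is the share of admitted subjects whose Screening and Day -1 values both exceed 5 x ULN. Multiplying by 15 gives the expected GB1211-treated subjects if the cohort were all of one sex.

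| ULN | Share, male | x 15 | Share, female | x 15 |
|---|---|---|---|---|
| 30 | 0.0016-0.0616 | 0.02-0.92 | 0.0002-0.0079 | 0.003-0.12 |
| 35 | 0.0002-0.0108 | 0.003-0.16 | 0 | 0 |
| 40 or more | 0 | 0 | 0 | 0 |

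The 0.92 arises only with an all-male cohort, median 80, between-subject CV 80% and within-subject CV 10%. A repeat of the simulation with another seed agreed to rounding; the all-male count at ULN 30 was below 0.5 in 13 of the 18 settings. AST, which has the widest band, was not simulated.

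**The case against.** The strongest reply is that no conflict has been shown, because its existence depends on a figure the documents do not contain. That stands, and it is why the point is conditional. The ceilings are each exactly five times a whole number and differ by sex and enzyme, which suggests they were written as 5 x ULN of one laboratory. This is inference only. If it is right, entry and stop were aligned by design, and the remaining weakness is that the alignment does not carry over to other laboratories.

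It can also be said that 4.8 is mandatory, so a subject with two pre-dose results above 5 x ULN would simply not be dosed. On that reading there is no exposure. But 4.8 speaks of stopping dosing, which can equally be read as applying only once dosing has begun. Then protection rests on criteria 14 and 25 and the Day -1 recheck. These are real safeguards, but none carries a number. Raised ALT is itself required for entry, so an Investigator could reasonably accept a value below the stated ceiling.

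Four stronger readings are tempting but not supported:

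- **That only bilirubin was matched to 4.8.** The bilirubin agreement is of the multiple alone: 4.8 has no stand-alone bilirubin stop. The pattern of the transaminase ceilings suggests they may have been matched too.
- **That section 3 supplies a low ULN** through "elevated alanine aminotransferase (ALT; defined as ALT values ≥ 30 U/L in males or ≥ 20 U/L in females". That phrase defines an entry floor and is not labelled a ULN, so no multiple should be built on it.
- **That 26 doses would necessarily be given.** This requires the narrower reading of 4.8, no intervention by the Investigator and no unscheduled test.
- **That Day 42 PK and biomarker data would necessarily be lost.** Section 4.8 lists withdrawal and permanent dosing stop separately and does not say that stopping the drug ends sampling.

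**Conclusion.** The concern holds in conditional form. At a Part C laboratory with a ULN below 31 (female ALT or AST), 37 (male ALT) or 40 U/L (male AST), the numeric entry criteria can admit a subject already above the 5 x ULN permanent stop. At 40 U/L or more there is no conflict.

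The break-even values are exact arithmetic. Whether any Part C laboratory falls below them is unknown. Under the assumed ALT distributions the expected count is well under one GB1211-treated subject in most settings, approaching one only in the extreme all-male case at a ULN of 30. The harm further depends on how 4.8 is read before the first dose and on the Investigator not acting. This is a low-severity point, worth settling because it concerns safety and is cheap to close before the optional Part C opens.

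**What to change.** Keep the present lines of criterion 4 and add one: *ALT or AST > 5 x ULN of the testing laboratory, confirmed by repeat (the Day -1 sample may serve as the repeat, with the result reviewed before the Day 1 dose)*. Leave 4.8 unchanged. When Part C sites are chosen, record each laboratory's ALT and AST ULN in the TMF.

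The threshold and the confirmation rule are the protocol's own, so no new clinical limit is introduced. The line can only lower a ceiling and has no effect at a ULN of 40 or more. It needs no new visit, no extra scheduled sample and no change in sample size.

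There are two costs. Under the ALT model above it excludes 0.2-6% of otherwise eligible men and 0.02-0.8% of women at a ULN of 30, and 0.02-1.1% of men and no women at 35; AST exclusions would add to this by an amount not estimated. It also requires Day -1 results to be available and reviewed before the first dose. The line does not exclude a subject just under 5 x ULN, or one whose repeat falls below it; whether to set a lower multiple is the sponsor's recruitment trade-off and is not proposed here.
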